Clinical Evaluation of the Sentosa® SA HSV1/2 Qualitative PCR Test

16 July 2014

Sponsor: Vela Research Singapore Pte. Ltd.

[name]

[name]

[name]

[name]

Confidentiality Notice

The information contained in this document is privileged and confidential. Distribution, copying, or disclosure is strictly prohibited unless required by federal regulations or state law.

Contact information

Study Sponsor: Vela Research Singapore Pte. Ltd.

[name]

[name]

[name]

[name]

Vela Project Manager: [name].

Vela Research USA, Inc.

[contact]

Email: [contact]

Clinical Study Manager: [name]

Radcliffe Consulting, Inc.

[name]

[name]

[contact]

email: [contact]

Study Monitor: [name]

[name]

[name]

[contact]

Clinical sites: TBD

Study Synopsis

Sponsor: Vela Research Singapore Pte. Ltd.

Device: Sentosa® SA HSV1/2 Qualitative PCR Test

Title of study: Clinical Evaluation of the Sentosa SA HSV1/2 Qualitative PCR Test

Number of sites: 3 external US sample collection sites and 3 testing sites; may be

same sites.

Study objective: The purpose of this study is to evaluate the performance of the

Sentosa SA HSV1/2 Qualitative PCR Test. Precision of results and concordance of results with a reference assay will be evaluated.

Study population & sample size:

This study will utilize residual samples from male and female patients with signs and symptoms of oral or genital HSV infections. Genital samples will include internal and external genital lesions such as those collected from lesions of the anus, buttocks, vagina, labia, or penis. Oral samples will include those collected from lip, gum, and mouth lesions.

For concordance testing, the sample size is based on historical study design and estimates of the expected prevalence of HSV1

and/or HSV2 in the population enrolled. For

Precision/Reproducibility testing, the sample size follows the CLSI

EP 5-A2 (2004) guidance document.

Study plan: Samples may be tested at the same facility at which they were

obtained, or may be shipped to a central laboratory for storage and redistribution to ensure adequate sample numbers at all testing sites. Testing will be done using the *Sentosa* SA HSV1/2 Qualitative PCR Test and the ELVIS® HSV ID and D³ Typing Test System

(reference assay).

Statistical analysis plan:

1.1 Background

Herpes Simplex viruses type 1 (HSV1) and type 2 (HSV2) are ubiquitous double-stranded neurotropic DNA viruses of the *Herpesviridae* family. Both HSV1 and HSV2 cause incurable lifelong infections. Infection results from inoculation of the virus through abraded skin or mucous membranes. Both viruses may remain latent for long periods and cause recurrent episodes of symptomatic disease.

HSV1 is transmitted primarily via oral secretions and non-genital contact. This results predominantly in infections of the oropharynx, face, eyes and central nervous system. In recent years the frequency of genital HSV1 infections has increased due to a lower rate of oral infection during prepubescent childhood, rendering individuals susceptible to genital infection in later life, and a rise in frequency of oro-genital contact. Nevertheless, seroprevalence studies show up to 80% of children infected with HSV1 by adulthood, with the highest rates among those in poor socioeconomic groups.

In contrast with HSV1, infection with HSV2 is usually the result of sexual transmission. In the United States, 20-25% of the population has antibodies to HSV2 by the age of 40, and there are at least 50 million people with genital herpes.³ In the majority of cases, symptoms are mild or unrecognized and the infection remains undiagnosed, although intermittent shedding of infectious virus into the genital tract still occurs. As a result, most transmission of genital herpes occurs through sexual contact with persons who are asymptomatic or unaware they are infected. Infection with HSV2 is more common in women than in men. HSV2 infection is linked to an increased risk of sexually transmitted human immunodeficiency virus (HIV).⁴ While transmission of the herpes virus to neonates *in utero* or intrapartum is rare, the consequences of such infections are severe and frequently fatal.

Classical primary genital herpes infection is preceded by localized pain or tingling, frequently accompanied by fever, malaise and inquinal lymphadenopathy. Within days, vesicles appear on the labia minora, introitus and urethra meatus of women and on the shaft and glans of the penis in men. The perineum and perianal areas may also be affected, as may the upper thighs and buttocks. Cervical lesions also occur frequently in women.

Primary infection with HSV1 cannot be distinguished clinically from that caused by HSV2, and the lesions may also be confused with those caused by other sexually transmitted diseases. As a consequence, laboratory testing is required for definitive diagnosis to reduce symptoms and hasten the healing of lesions. In addition, because the recurrence of HSV1 infections and subclinical shedding are less frequent than for HSV2, determination of the etiology of infection and typing of the virus is useful in the

assessment of prognosis and counseling.^{1,2,5,6} Historically, the preferred method of diagnosis of herpes infection has been viral isolation in tissue culture followed by type-specific immunofluorescent detection. The enhanced sensitivity, robustness, and rapid time to results of amplification methods for the detection of viral DNA are leading to their increasingly widespread adoption.^{1,3,6}

The Sentosa® SA HSV1/2 Qualitative PCR test is a polymerase chain reaction (PCR)-based qualitative *in vitro* diagnostic test for detection and typing of Herpes simplex virus (HSV) DNA using genital or oral samples. The assay includes a set of oligonucleotide primers and dual-labeled, linear, sequence specific hydrolysis probes for use in real-time PCR assays on the Sentosa SA201. The Sentosa SA201 instrument is a real-time PCR cycler with 5 channels. The Sentosa SA HSV1/2 Qualitative PCR assay uses 3 of the 5 available channels.

The assay kit consists of real-time PCR master mix (MM), primers and probes mixture (PPM), negative control (NC), extraction control (EC) and positive control (PC). There are two sets of primers and three sets of probes for detection of HSV1, HSV2, and extraction control nucleotides, and the amplifications of the targets in 3 channels (green, orange and red) on the *Sentosa* SA201 instrument. Output is recorded as the increase of fluorescence over time in comparison to background signal.

1.2 Principle of the procedure

Pathogen detection by PCR is based on the amplification of specific regions of the pathogen genome. In real-time PCR, the amplified product is detected via fluorescent dyes, which are usually linked to oligonucleotide probes that bind specifically to the target sequences. Real-time monitoring of the fluorescence intensities during the PCR run allows the detection of the accumulating product.

2. Description of the device

2.1 Overview

The Sentosa SA HSV1/2 Qualitative PCR Test workflow starts with extraction of nucleic acids from samples (genital or oral swabs in Universal Viral Transport Medium; VTM) using the Sentosa SX Virus Total Nucleic Acid Kit on the Sentosa SX101 instrument. After extraction, the instrument will set up the PCR with the extracted nucleic acids automatically in the 96-well PCR plate. Subsequently, the 96-well PCR plate is sealed and transferred to the Sentosa SA201 instrument for PCR amplification, followed by data analysis. Refer to the user manual for a detailed description.

2.2 Description of the test system

The Sentosa SA HSV1/2 Qualitative PCR Test is a ready-to-use system for the detection and differentiation of HSV1/2 DNA in genital or oral swabs in VTM. Nucleic acid extraction from clinical specimens and PCR set-up are performed on the Sentosa SX101, an automated liquid handling and sample preparation system. PCR is done on

the Sentosa® SA201 instrument. The HSV1/2 master mix contains reagents and enzymes for specific amplification of a 104 base pair (bp) fragment of the *UL30* gene common to both HSV1 and HSV2. The master mix also contains specific probes for the direct detection and differentiation of HSV1 and HSV2 amplicons in the fluorescence channels Cycling Green and Cycling Orange of the Sentosa SA201 instrument.

In addition, the *Sentosa* SA HSV1/2 Qualitative PCR Test contains a third set of primers/probes designed to detect an extraction control (EC) target in the fluorescence channel Cycling Red. This extraction control is used as control for the nucleic acid isolation procedure and as a PCR inhibition control. The extraction control amplification does not compromise the detection limit of the HSV1/2 PCR amplification. The test also contains a negative control (NC) and a positive control (PC) that allow the user to assess whether the PCR reaction has been performed properly.

The following is an overview of the system workflow.

- 1. Prepare samples.
- 2. Scan samples using Sentosa Link, which generates an entry list file.
- 3. Import entry list file to Sentosa SX101 software.
- 4. Load consumables, reagents, controls and samples onto the Sentosa SX101.
- 5. Select relevant application and start the run.
- 6. After run is completed, remove and seal the 96-well PCR plate.
- 7. Sentosa SX101 software generates ".smp" file.
- 8. Sentosa Link transfers ".smp" file from Sentosa SX101 to Sentosa SA201 instrument.
- 9. Transfer the 96-well PCR plate into the Sentosa SA201 instrument chamber.
- 10. Import ".smp" file and define the PCR run, then start the PCR run.
- 11. After the run is completed, *Sentosa* SA series software analyzes result and *Sentosa* SA Reporter software interprets results.
- 12. Sentosa Link reads and displays the results.

2.2.1 Sentosa® SX101

The Sentosa SX101 is an automated pipetting system that provides an easy-to-use workflow for nucleic acid extraction and PCR setup for up to four assays simultaneously (Figure 1).

The Sentosa SX101 system operates as follows: liquid (samples from the source tube) is transported via pipette tips to the destination tube. An optical sensor automatically checks the correct selection and positioning of tubes, available supplies (labware), and the position of pipette tips in the rack.

Figure 1. Sentosa® SX101

The Sentosa SX101 instrument has the following features:

- Software-controlled thermo-mixer module for mixing, heating and cooling of samples, and for supporting the magnetic beads-based Sentosa SX Virus Total Nucleic Acid Kit:
- Preset in vitro diagnostic (IVD) protocol for the Sentosa SA HSV1/2 Qualitative PCR Test;
- Color matching of tube holders and reagent caps, ensuring correct placement of reagents;
- Inscribed names, providing further assurance on the correct positioning of reagents;
- Integrated workflow with barcode identification (ID) tracking functionality to ensure sample traceability from start to end of workflow;
- Barcoding of tubes containing the samples to reduce error rates due to manual input of information; and
- Optical sensor scanning of the deck before each run to ensure the correct number and types of tips and labware.

2.2.2 Sentosa® SA201

Sentosa SA201 is a real-time nucleic acid amplification and detection system that measures nucleic acid signals and converts them to comparative quantitative readouts using fluorescent detection of dual-labeled, linear, sequence specific hydrolysis probes.

The thermocycler is in 96-well format and the 5-colour detection system enables the use of a wide range of fluorophores (dyes). Ten dyes are calibrated as part of the standard installation of the Sentosa® SA201: FAM, SYBR Green I, JOE, VIC, NED, TAMRA, Cy3, ROX, Texas Red and Cy5. The Sentosa® SA HSV1/2 Qualitative PCR Test will use the following four dyes: FAM, JOE, ROX and Quasar 670. Quasar 670 is used as a substitute for Cy5 in the Sentosa® SA HSV1/2 Qualitative PCR Test. A calibration procedure will be provided by Vela for the use of Quasar 670, which will be part of the standard recommended calibration procedure for this test. The Sentosa SA201 is shown in Figure 2.

Figure 2. Sentosa SA201

2.3 Workflow

The Sentosa SA HSV1/2 Qualitative PCR Test workflow starts with extraction of nucleic acids from samples (genital or oral swabs) using the Sentosa SX Virus Total Nucleic

Acid Kit on the *Sentosa* SX101 instrument. After extraction, the instrument automatically sets up the PCR with the extracted nucleic acids in the 96-well PCR plate. Subsequently, the 96-well PCR plate is sealed and transferred to the *Sentosa* SA201 for PCR amplification, followed by data analysis.

Drivers are installed on the *Sentosa*[®] Link to connect the *Sentosa* SX101 instrument and the *Sentosa* SA201. This creates a user environment that links the SX101 and the *Sentosa* SA201 to facilitate automatic workflow to export results in a LIS/LIMS-compatible format.

2.4 Calibrators and controls

The control set for the *Sentosa* SA HSV1/2 Qualitative PCR Test is provided in the assay kit for each set of assay reagents. One positive and one negative control must be included for each batch of samples and for new reagent kits. Controls must be positioned according to the *Sentosa* SX101 Instrument User's Manual. The HSV positive control is a mixture of two linearized plasmids and monitors for substantial reagent failure, as well as instrument and workflow, and inhibition due to instrument or workflow failure. The HSV negative control monitors for reagent and/or environmental contamination.

The extraction control (EC) oligonucleotide is used to confirm the validity of the extraction process. The EC is supplied as a liquid in extraction tubes and can be loaded directly onto the *Sentosa* SX101 platform. During the automated procedure, the EC is added directly into lysis buffer for PC, NC and sample extraction. At the end of the extraction process, the EC fluorescence is monitored by the instrument and an automated algorithm is applied to both the EC and the HSV specific signals to report sample results as positive, negative, or EC failure.

2.5 Reference assay

The reference assay to be used in this evaluation is the ELVIS[®]HSV ID and D³ Typing Test System (K091753), manufactured by Diagnostic Hybrids. The product code for this assay system is OQO.

3. Intended Use

The Sentosa SA HSV1/2 Qualitative PCR Test is a multiplex, real-time PCR-based qualitative in vitro diagnostic test for detection and typing of herpes simplex virus type 1 (HSV-1) and type 2 (HSV-2) DNA from male external and internal genital lesions, female external (anogenital) and internal (vaginal) lesions, or external and internal oral lesions. The test is intended for use as an aid in the diagnosis of HSV infection in symptomatic patients.

Warning: The *Sentosa* SA HSV1/2 Qualitative PCR Test is not FDA cleared for use with cerebrospinal fluid (CSF). The assay has not been established for antiviral therapy and is not intended for prenatal screening.

4. Study materials

4.1 Materials supplied by the sponsor

Vela Research USA will supply the following reagents and equipment and its associated software to each testing site:

- Sentosa SX101 instrument for extraction and PCR set-up;
- Sentosa SA201 for real time nucleic acid amplification and detection;
- Sentosa Link software:
- Sentosa SA201 Series software:
- Sentosa SA Reporter;
- Sentosa SX Virus Total Nucleic Acid Kit;
- Sentosa SA HSV1/2 Qualitative PCR Test;
- Sentosa SX Safe-Lock Tubes;
- Sentosa SX Partition 50µL Filter Tips;
- Sentosa SX Partition 1000µL Filter Tips;
- Sentosa SX 100mL Reservoir;
- Sentosa SX 30mL Reservoir;
- Sentosa SX Deepwell Plates 96/2000µL
- Sentosa SX Rack for 96 1.5/2.0mL Screw Tubes;
- Sentosa SX Microplates 96/V;
- Sentosa SX Biohazard Bag;
- Sentosa SX PCR Foil, adhesive;
- Sentosa SX Thermoblock PCR 96;
- Sentosa SX Dispensing tool TM 50
- Sentosa SX Thermoblock PCR 96
- MicroAmp[®] Splash-free Support Base;
- MicroAmp[®] Fast Optical 96-Well Reaction Plate with Barcode, 0.1 mL;
- MicroAmp[®] Optical Adhesive Film.

4.2 Equipment and Materials supplied by the clinical site

The clinical site will provide all miscellaneous laboratory supplies, including nitrile gloves, 1% (v/v) sodium hypochlorite, pipettes capable of transferring 0.5 mL, pipette tips with filters, a vortex mixer, a bench top centrifuge, 96-well PCR plate centrifuge, and saline (0.9% NaCl).

In addition, the clinical site will ensure there is adequate bench space for all instrumentation supplied by Vela Research USA, maintained at required conditions as stated in the Instructions for Use. Also, the clinical site will ensure there is adequate

secure storage space for all supplies used in the clinical evaluation, including refrigerated space as needed.

The clinical laboratories that participate in this study as testing sites will be required to have the reference assay installed and qualified for use, with appropriate quality assurance procedures in place.

4.3 Investigational product accountability

The clinical investigator at each site, or a responsible designee, must maintain an inventory record of all materials and supplies received from the sponsor. All investigational device materials and supplies may be used only for the purposes stated in this protocol. Forms will be supplied to the sites for inventory control, including receipt, usage/disposition, and return of all investigational materials and supplies. Loss of investigational materials or supplies due to wastage or other reason must be documented with the name of the responsible individual, date, and quantity.

4.4 Investigational product disposal or return

Upon completion or termination of the study, all unused investigational materials and supplies must be returned to the sponsor or disposed of at the clinical site. Disposal requires written authorization from the sponsor. Return and/or disposal must be documented as described in section 4.3, above.

5. Sample acquisition

5.1 Sample inclusion criteria

Samples may be included in the assay validation if they meet the following criteria:

- Sample was taken from a lesion from an internal or external oral or genital site.
- Sample was submitted to a clinical laboratory for the purpose of testing for the presence of HSV1 or HSV2.
- The following information about the patient from which the sample was taken is available:
 - o presumptive diagnosis or signs and symptoms causing assay requisition,
 - o site of lesion,
 - o age at time of sample collection or date of birth, and
 - o sex.
- Samples were collected in universal viral transport media, using a plastic shaft swab made of either polyester, cotton, rayon or Dacron.
- There is sufficient residual sample to perform both test and reference assays.

5.2 Sample exclusion criteria

If a sample meets any of the following criteria, it must not be included in the assay validation:

- Sample leaked during shipment or storage prior to assay.
- Sample has undergone more than 1 freeze-thaw cycle before testing;
- Sample eluent is not clear after centrifugation (refer to section 6.3.1).
- Sample ID is missing or ambiguous.
- Sample is collected using alginate calcium swab.
- Sample handling and storage requirement in section 5.4 not followed

5.3 Sample collection

The samples used in the study will be residual material from female and male genital samples collected for clinical HSV1/2 testing from anal, buttock, vaginal, labial, or penile lesions, or oral swab samples collected from lesions of the lips, gums or mouth. The specific lesion site will be identified on the case report form for each sample.

Each sample will be de-identified to ensure there is no link to patient identity, and labeled with a study ID according to the following scheme:

XX-ZZZ, where XX represents the clinical site (e.g., 01, 02), and ZZZ represents the consecutively numbered sample acquired at each clinical site.

Sample barcode labels must be printed out and attached to the tube.

The total sample collection period of this study is 1 to 2 months. The target number of samples is 585 oral samples and 495 genital samples.

The clinical sample set may be enriched with contrived positive samples where virus is spiked into either negative clinical matrix or VTM.

5.4 Sample handling and storage

All samples should be treated as infectious biological material. Study ID must be securely affixed to the study sample; if the study ID is missing or ambiguous the sample may not be used in the study. Samples to be used in this study must be segregated from all other samples, in separate racks, both during testing and when stored.

- Store at room temperature (15°C to 25°C) if samples will be processed for Sentosa testing (i.e., extraction) within 4 hours after accession in the lab.
- Store at 4°C if samples will be processed for Sentosa testing within 72 hours of accession in the lab.
- Store at -70°C or lower temperature for long-term storage (up to 1 year).
- Only fresh samples (stored at 4°C) will be tested with ELVIS within 72 hours of accession in the lab.

• Testing via Sentosa® SA HSV1/2 Qualitative PCR Test should be completed on samples that have undergone similar storage conditions to ELVIS or no more than 1 freeze thaw cycle.

Temperature logs for all storage facilities will be maintained, including room temperature for days on which assays are run.

6. Study plan

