6.2.3 Concordance

For concordance testing, a minimum of 585 oral samples and 495 genital samples will be collected at 3 clinical sites. Each site will test at least 195 oral samples and 165 genital samples.

Samples will be tested using the investigational device and the reference assay in parallel (testing initiated on the same day from the same sample) by a qualified technician who has been specifically trained to participate in the study. Results will be sent to the study manager for review; the clinical site will be notified if any samples must be retested. Residual sample may be stored after initial testing following storage requirements in section 5.4 until retest notification has been received.

Samples that yield discordant results between the investigational and reference methods will be re-tested by Vela Research USA, using different PCR primers and bidirectional sequencing. Results from discrepant testing will be reported as a footnote in the package insert. Only samples containing sufficient volume will be retested for discrepant analysis.

Any sample left after all testing is completed should be frozen at -70°C for shipment to Vela Research USA.

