6.3.1 Sample processing procedure

Sample material present on a swab will be eluted by vigorous agitation (i.e., vortexing) of the transport tube. The swab should then be discarded as biohazardous waste. Only clear sample eluent may be used as inoculum. If visual precipitates are observed, the eluent should be centrifuged at 4000 rpm for 10 minutes; the clear supernatant should be collected as inoculum. If centrifugation does not exclude precipitate the sample will be considered contaminated.

All frozen samples (sample eluent) must be allowed to thaw completely at room temperature and must be mixed by inversion.

During the procedure 250 µL of sample is transferred into a fresh 1.5 mL *Sentosa*[®] SX Safe-Lock Tube with proper label, in a biosafety cabinet, for sample loading of *Sentosa* SA HSV1/2 Qualitative PCR Test.

6.3.2 Procedure of Sentosa SA HSV1/2 Qualitative PCR Test.

Refer to the reference user manual of *Sentosa* SA HSV1/2 Qualitative PCR Test for detailed work instructions.

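### Section 5.4 allows Sentosa testing after one freeze-thaw cycle while ELVIS needs fresh sample, without limiting this to repeat tests; for first concordance tests this conflicts with the same-day rule in 6.2.3

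*Combined protocol and SAP*

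**What the plan says.** All references are to the combined protocol and SAP.

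- **Reference assay, 5.4:** "Only fresh samples (stored at 4°C) will be tested with ELVIS within 72 hours of accession in the lab". No frozen option is given for ELVIS.
- **Test assay, 5.4:** Sentosa testing should be completed on "samples that have undergone similar storage conditions to ELVIS or no more than 1 freeze thaw cycle". The same section provides for frozen storage: "Store at -70°C or lower temperature for long-term storage (up to 1 year").
- **Exclusion criteria, 5.2:** a sample is excluded if "Sample has undergone more than 1 freeze-thaw cycle before testing". One cycle is therefore acceptable.
- **Concordance testing, 6.2.3:** the two assays are to be run "in parallel (testing initiated on the same day from the same sample"). The section goes on to let residual sample be kept under the 5.4 rules after initial testing, until the site hears whether a retest is needed.
- **Sample processing, 6.3.1:** frozen eluents "must be allowed to thaw completely at room temperature and must be mixed by inversion". This is a general step, not tied to first or repeat tests.
- **Synopsis, study plan:** samples "may be shipped to a central laboratory for storage and redistribution", to even out numbers across testing sites. Neither a storage temperature nor a time limit is given.
- **Analysis plan, 7.2:** agreement is tabulated by virus and site, with female external and internal genital samples shown separately. There is no breakdown by storage state. Equivalence needs sensitivity above 92.5% and specificity above 93.6%, for both viruses, at two or more of the three sites.

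**The concern.** In 5.4 the word joining the two Sentosa conditions is 'or', so a once-frozen sample is a full alternative to one stored like the ELVIS sample. A site could run ELVIS on the fresh sample, freeze the remainder, and run its first Sentosa test weeks later. That complies with 5.4 and 5.2 but breaches the same-day rule in 6.2.3. The plan does not say which section governs.

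For such a sample the comparison is a fresh reference against a stored test. If freezing and thawing costs detectable target, the loss is counted as a miss by the device, and storage and assay performance can no longer be separated. Table 1 in 7.2 would combine these results with same-day fresh pairs. The plan has no sensitivity analysis by storage state and no restriction to fresh pairs that would reveal the problem. Success is judged on point estimates at single sites, so a modest shift in sensitivity can matter.

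**Working it through.** **Step 1. Setting the rules side by side, for a first concordance test**

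| Rule | ELVIS | Sentosa |
|---|---|---|
| 5.4 | fresh, 4°C, within 72 hours of accession | similar storage to ELVIS, or up to one freeze-thaw cycle |
| 5.2 | no separate rule | excluded only above one cycle |
| 6.2.3 | same day, same sample as Sentosa | same day, same sample as ELVIS |

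A sample fresh enough for ELVIS and run on Sentosa that same day would not normally have been frozen in between. Freezing and thawing within one day is literally possible, but it is not what storage for up to a year describes. A frozen aliquot is still the same sample, so the conflict is with the same-day element of 6.2.3.

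For a repeat test there is no conflict: 6.2.3 provides for storage under 5.4 after initial testing.

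**Step 2. How large could the effect be?** The plan has no figure of its own to reproduce here. The inputs are:

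- Threshold: sensitivity above 92.5% at two or more of three sites (7.2).
- Reference positives per site for one virus: n = 73. This is an assumption. Section 7.1 gives 73 as the minimum per analysis group but does not say that this means reference positives for one virus at one site.
- Sensitivity on fresh sample: 95%. This is an assumption, set equal to the minimal acceptable concordance in 7.1.
- Share of reference positives frozen before the first Sentosa test, w, and proportion of detections lost to freeze-thaw, L: neither is in the documents, so both are varied.

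Formulas:

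- Observed sensitivity: p = 0.95 × (1 − L × w).
- Pass mark at a site: 0.925 × 73 = 67.5, so at least 68 detections are needed (68/73 = 93.2%; 67/73 = 91.8%).
- Chance of passing at one site: q = P(X ≥ 68), X binomial with n = 73 and probability p.
- Chance of passing at two or more of three sites: 3q²(1 − q) + q³.

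| L | w | p | q | Two or more of three sites |
|---|---|---|---|---|
| 0 | any | 95.0% | 0.842 | 93% |
| 2% | 10% | 94.8% | 0.822 | 92% |
| 5% | 10% | 94.5% | 0.790 | 89% |
| 2% | 50% | 94.1% | 0.733 | 82% |
| 5% | 50% | 92.6% | 0.546 | 57% |

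For example, with L = 5% and w = 50%, p = 0.95 × (1 − 0.025) = 0.926 and q = 0.546. The chance is then 3 × 0.546² × 0.454 + 0.546³ = 0.406 + 0.163 = 0.57.

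These chances are for one virus and for sensitivity only; they do not cover specificity or the requirement that both viruses pass.

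**The case against.** The strongest reply is that the sections can be read together. Section 6.2.3 is the specific rule for concordance testing and 5.4 is a general storage section. Section 6.2.3 itself sends residual sample into 5.4 storage pending retest notification, and 6.3.4 lists many reasons for repeat testing, such as invalid samples and machine failure. The one-cycle limit in 5.2 and the thawing step in 6.3.1 serve retests equally well. On this reading, first tests are run fresh and in parallel, and one freeze-thaw cycle is tolerated only afterwards. This is plausible and may be what was intended. It does not dispose of the point, because no section says so and the wording of 5.4 and 5.2 reaches first tests as well.

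The reply does rule out some stronger inferences that a reader might draw:

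- **That every use of the freeze-thaw allowance breaches 6.2.3.** It does not; a frozen retest is compatible with that section.
- **That frozen first testing is planned.** The synopsis mentions central storage and redistribution but not freezing. Since ELVIS needs fresh sample, redistributed samples still awaiting ELVIS would have to stay fresh.
- **That a delayed Sentosa run is open to reader bias because the ELVIS result is known.** Sections 2.2 and 2.4 describe automated calling and software interpretation of Sentosa results, which leaves little room for this.
- **That the narrow gap between 68 and 67 detections shows a storage effect.** That gap exists at n = 73 however the samples were stored.
- **That the plan favours the device on sensitivity.** Loss of target lowers apparent sensitivity, so the risk shown here is of the device failing, not of a flattering result.

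**Conclusion.** The point stands as a conflict in the text that can reach the main analysis. Section 5.4, with 5.2, permits a once-frozen first Sentosa test against a fresh ELVIS test; 6.2.3 does not; and 7.2 would pool the result without identifying it.

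The numerical effect is conditional. It arises only if the frozen route is used for first tests and freezing costs detections, and the documents quantify neither. Under the stated assumptions it runs from about one to four percentage points in the chance of meeting the sensitivity criterion with a tenth of samples frozen (93% to 92% or 89%). With half frozen it is 11 to 36 points (93% to 82% or 57%). If the loss is near zero it is negligible. A scenario with all samples frozen would need 6.2.3 to be ignored throughout, so it is not a reasonable basis for judging size.

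This should be corrected before testing starts, because storage state that is not recorded at the time may not be recoverable later. Confidence is medium, given the plausible retest reading.

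**What to change.** Reconcile 5.2, 5.4, 6.2.3 and 6.3.1 so that they state one rule:

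1. For concordance, the first Sentosa and ELVIS tests are run from the same fresh sample, on the same day, within the 72-hour window.
2. The allowance of one freeze-thaw cycle applies to repeat and discrepant testing only. The exclusion in 5.2 and the thawing step in 6.3.1 should be worded to match.
3. Storage state at testing is recorded for every result.
4. In 7.2, if any first Sentosa result nevertheless comes from a frozen sample, agreement is reported by storage state, with the same-day fresh pairs shown separately.

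The cost is a few sentences of protocol text, one extra data field and possibly one extra table. The downside is that samples that cannot be run fresh may not count as same-day fresh pairs, which could mean collecting more samples or relying less on central redistribution.
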